5.3.2 INCIDENT REPORTING

(Serious) incidents must be documented in an incident report form (available online from BfArM) and reported via online platform to the BfArM.

5.4 AUDITING

The BMBF or its representatives may perform audits or inspections.

6. ETHICS AND DISSEMINATION

6.1 RESEARCH ETHICS APPROVAL

The study was developed and will be conducted in accordance with the principles stated in the Declaration of Helsinki and subsequent amendments and in accordance with the Guidelines for Good Clinical Practice (ICH Topic E 6 (R1)).

An ethical approval application together with the ICF, study information and any other requested documentation has been submitted to the responsible EC of the Charité - Universitätsmedizin Berlin. The study received EC approval on 07.04.2022 (EA4/043/22).

6.2 PROTOCOL AMENDMENTS

Substantial amendments to the protocol will be submitted to the EC. The investigator is responsible for informing the EC of all problems involving risks to residents. If changes in the ICF become necessary, these documents must be submitted to the EC as well. Changes will be filed in the ISF.

6.3 CONSENT OR ASSENT

The investigator is obliged to give full written and verbal information to the residents/patients and if applicable their legal representatives about the nature of the study, its purpose, the procedures involved, the expected duration, potential risks and discomforts as well as about the right to discontinue participation in the study without affecting their further relationship with the investigator or their future care.

Prior to inclusion into the study, the consent for each participating subject must be obtained on a written statement (ICF) which is approved by the EC. The ICF has to be written in national language and an easily understanding target group adapted wording has to be used. Two original ICFs must be personally dated and signed by the residents/patients or if applicable by their legal representatives. In all cases, the Investigator must also personally date and sign the original ICFs and confirm by this way that he/she has provided all information regarding this study. One original is intended for the resident/patient and the other one for the ISF.

The signed ICF must be obtained before engaging any study-related procedure with the resident/patient or data collection. The information and consent procedure is the responsibility of the investigator. The investigator can delegate qualified study team members to obtain the informed consent.

6.4 INSURANCE

All subjects enrolled in this study are covered against negligent conduct of the Investigator or study assistants by the liability insurance of the Charité - Universitätsmedizin Berlin.

6.5 CONFIDENTIALITY AND DATA PROTECTION

All personal information about potential and enrolled participants is confidential. This ensures the strictly split between the personal data and participant-related dataset (trial data).

A pseudonym is generated for every new participant. The pseudonym will be a combination of two characters (GH for participants in geriatric hospitals/wards; NH for participants in the nursing homes) and three numbers with ascending sequence (001 to 250). All trial data of the resident will be linked with this pseudonym. Personal data of the resident will not be saved in the trial database at any time.

The investigator affirms and upholds the principle of the participant's right to protection against invasion of privacy. Throughout this study all data recorded or passed on for further evaluation will be coded by the randomization number. Identification is restricted to authorized persons. Participant's data may be stored and electronically processed by the investigator for a scientific purpose. This study will comply with the requirements of the Berliner Datenschutzgesetz (BlnDSG), the General Data Protection Regulation (GDPR; EU 2016/679) and the Kirchengesetz über den Datenschutz der Evangelischen Kirche in Deutschland (EKD).

6.6 DECLARATION OF INTERESTS

The principal investigator declares, that he has no financial or competing interests for the overall trial.

6.7 ACCESS TO DATA

All study-related information will be stored securely at the Institute for Clinical Nursing Science. All information regarding the participants will be stored in locked file cabinets in areas with limited access. Electronically data (e.g. photographs) are stored on a secured digital server of the Institute for Clinical Nursing Science.

The investigator:

1. Ensures that the study is conducted in accordance with the protocol and the applicable ethical and regulatory requirements and that all data generated during the study are accurate, relevant and valid and are entered into the SD;
2. Keeps an ISF in order to ensure filing and subsequent archiving of all relevant study documents during and after the study (original protocol, ethics committee approval and administrative documents, etc.);
3. Retains a subject identification list containing the participants names, addresses and randomization numbers to allow checking of data reported on CRFs with those from SD;
4. Enables direct access to SDs for monitoring, audits and inspections, thus ensuring accuracy of the data (if applicable). All representatives that have been granted access to the data documentation to perform quality monitoring/audit keep professional confidentiality with regards to the participant's data.

The Investigator is responsible for ensuring that all study records, including SD, ISF, signed ICFs, and the subject identification list are archived for the period of time required by law.

6.8 ANCILLARY AND POST-TRIAL CARE

Ancillary and post-trial care will not be provided.

6.9 DISSEMINATION POLICY

Results dissemination will start with registration at Clinicaltrials.gov and at the DRKS before enrollment of the first participant. In addition, the trial protocol will be published in the journal 'Trials' or any other comparable open access journal. After study completion, results will be uploaded at clinicaltrials.gov and published in international journals and at least in one German journal (e.g. 'Pflege'). All articles will be published open access. Results will be further presented at national and international conferences. To support dissemination of the trial results for subsequent research purposes (e.g. individual-patient data (IPD) meta-analyses or secondary analyses), we will provide access to anonymized IPD from this trial according to the recommendations of the International Committee of Medical Journal Editors (ICMJE) [39]. It is planned to share the data at zenodo.org supported by the European Commission.

VI. REFERENCES

- [3] Van Damme N, Van den Bussche K, De Meyer D, Van Hecke A, Verhaeghe S, Beeckman D. Independent risk factors for the development of skin erosion due to incontinence (incontinence-associated dermatitis category 2) in nursing home residents: results from a multivariate binary regression analysis. *Int Wound J.* 2017;14:801-10.10.1111/iwj.12699.

Intervention therapy:	Intervention arm I: Standardized mild skin cleansing regimen and daily topical application of a film-forming skin protectant at the exposed skin areas. Intervention arm II: Standardized mild skin cleansing regimen and daily topical application of a hydrophobic skin protectant at the exposed skin areas.
Control therapy:	Standardized mild skin cleansing regimen without application of an additional skin protectant
Study population:	Incontinent geriatric patients
Sponsor:	Charité - Universitätsmedizin Berlin, [name]
Financial support:	Federal Ministry of Education and Research (Bundesministerium für Bildung und Forschung (BMBF)) by grant number 01KG2020.
Protocol registry identification:	DRKS00028954
Clinical phase:	Randomized controlled, parallel group, three-arm, assessor-blinded exploratory trial

Approved by

[name]. rer. cur. [name]
Name, Principal Investigator

Place, Date, Signature

Dipl.-Math. [name]
Name, Statistician

Place, Date, Signature

PD Dr. phil. [name]
Name, Statistician

Place, Date, Signature

Dr. rer. medic. [name]
Name, Trial Coordinator

Place, Date, Signature

File history

Version	Date	Major changes	Comment
01	01/14/2025		Initial SAP
02	03/20/2025	
 Erythema level 1 and 2 reporting Exclusion of feasibility assessment Analysis of erosion: no adjustment for baseline Correction of cognitive condition for patient satisfaction assessment Specification of timepoints for secondary outcome assessments Addition of location (front/back) for subgroup analyses 	
The mean of Erythema levels 1 and 2 will be aggregated and analyzed as endpoint
 
The percentage of eligible individuals who were willing to participate could not be assessed.
 
Erosion at baseline was exclusion criterion
 
If IAD present and MMSE ≥ 24
 
If IAD present
 
For Erosion
 
Remark: additional minor changes (formatting, spelling and grammar)

03	04/15/2025	
 Flow chart adjustment Enumeration of participating wards Clarification on patient satisfaction measurement 	
The flow chart was modified and now includes updated information on participant flow, and exclusions; starting from the set of included subjects.
 
The number of nursing homes and the respective participant counts have been added
 
Patient satisfaction was measured at each visit day if MMSE ≥ 24, regardless of IAD presence
 
Remark: additional minor changes (formatting, clarifications)

04	04/16/2025	
 Adding the secondary analysis for patients with no initial IAD 	
Additional subgroup analysis
 
Remark: additional formatting

Abbreviations

AE	Adverse Event
BlnDSG	Berliner Datenschutzgesetz
BMBF	Bundesministerium für Bildung und Forschung
BMI	Body Mass Index
CRF	Case report form
CTO	Clinical Trial Office at the Charité
DMP	Data management plan
DRKS	Deutsches Register Klinischer Studien (German Clinical Trials Register)
DSGVO	Datenschutzgrundverordnung (General Data Protection Regulation)
EC	Ethics committee
EU	European Union
eCRF	Electronic case report form
GCP	Good Clinical Practice
GDPR	General Data Protection Regulation
GDS	Global Deterioration Scale
GLOBIAD	Ghent Global IAD Categorization tool
IAD	Incontinence associated dermatitis
ICD	International Classification of Diseases
ICF	Informed consent form
ICH	International Conference on Harmonization
ICMJE	International Committee of Medical Journal Editors
IPD	Individual patient data
ISF	Investigator Site File
IIT	Investigator Initiated Trial
ITT	Intention-to-treat
MDR	Medical Device Regulation
MPDG	Medizinproduktegesetz-Durchführungsgesetz
NRS	Numeric Rating Scale
PU	Pressure Ulcer
QoL	Quality of life

RDE	Remote Data Entry
SAE	Serious Adverse Event
SAP	Statistical analysis plan
SAS	Statistical analysis system
SD	Source documents
SGB	Sozialgesetzbuch (Codebook of Social Law)
SOP	Standard operating procedure
SPSS	Statistical Package for the social science
SSL	Secure Sockets Layer
WHO	World Health Organization

1 Background

Incontinence-associated dermatitis (IAD) is an unwanted skin condition which is common in incontinent individuals. It is an inflammatory skin response due to repeated or prolonged contact with urine and/or stool [1, 2]. It can occur throughout the lifespan; thus, it is present in babies and young children ("diaper dermatitis") as well as in the older individuals [1].

The prevalence of incontinence rises with increasing age [3]; therefore, IAD is more common in aged populations. IAD prevalence is 3% to 23% in long-term geriatric care and 15% to 40% in acute care settings [4]. A representative prevalence study in institutional geriatric long-term care facilities showed an IAD prevalence of 35.4% [5, 6]. Thus, around one in three residents was affected by some form of IAD.

Clinically, IAD is manifested by skin redness, vesicles, nodular thickening and maceration of the tissue as well as defects of the skin up to the loss of the upper skin layers. For those affected, this can be a physical as well as psychological burden. In addition to pain, burning, and itching, IAD is associated with an increased risk of secondary infections and the development of pressure ulcers (PUs) [7, 8]. As a result of these changes, affected individuals may also suffer from a reduced quality of life, for example, through a loss of independence, reduction of social activities, or poor sleep due to IAD-related pain or itch [6, 9, 10].

With approximately 80%, the majority of residents in geriatric long-term care facilities, as well as a high proportion of geriatric patients in acute care settings, are affected by one form of incontinence and are therefore at potential risk of developing IAD [11-13]. If adequate preventive measures are taken at an early stage, IAD might be avoided. However, the high prevalence of IAD in these settings indicates that current prevention strategies are not optimal. Due to a lack of knowledge, the current nursing practices in the context of IAD prevention are mainly influenced by individual traditions and personal preferences and are not evidence-based [14]. At the same time, a clear need for support as well as assistance is expressed on the part of nurses and other caregivers in order to be able to perform an efficient and effective IAD prevention [15]. Therefore, it is an important aim to close existing evidence gaps in this area to support nurses and other caregivers with a solid scientific base for IAD prevention. The planned trial aims a direct comparison of the two most important skin protection product categories in the form of an explorative randomized controlled trial (RCT), taking core outcomes for IAD research into account.

1.1 Trial objectives

1.1.1 Primary objective

The primary research objective is to compare the incidence of IAD in two intervention groups and one control group and to estimate effect sizes for a possible subsequent confirmatory RCT.

1.1.2 Secondary objectives

Additional objectives are to test the feasibility of conducting a confirmatory RCT to prevent IAD and to evaluate the feasibility of measuring the Core Outcome Domains for IAD trials.

The trial will answer the following research questions:

- What are the effect sizes of the outcomes when comparing the intervention groups and the control group?
- Is the implementation of a standardized skin protection regime for the prevention of IAD feasible in geriatric hospital wards and nursing homes?
- Does the implementation of a standardized skin protection regime for the prevention of IAD reduce IAD-related itch and IAD-related pain?
- Is the measurement of Core Outcome Domains for IAD trials feasible?

1.2 Trial design

The trial is designed as a randomized controlled (ratio 1:1:1), parallel group, three-arm, assessor-blinded exploratory trial. Patients are randomized stratified by sex (male/female) into the treatment arms. The study was conducted in geriatric hospitals/geriatric wards of participating hospitals and in institutional long-term care facilities of the federal state of Berlin, Germany.

2 Analysis sets

2.1 Definitions

Intention-to-treat/Full analysis population

The full analysis set (FAS) contains all participants that met the inclusion criteria and were randomized, irrespective of possible protocol deviations, discontinuation of the study treatment or withdrawal from the study by the subject. Study participants will be categorized according to the intended treatment. As only exception, the following reasons cause an exclusion of participants from the full analysis set: (I) No treatment was applied at all or (II) there are no data available after the subject's randomization. Subjects excluded from the full analysis set will be mentioned in the study report and reasons for exclusion will be documented per group. In case of consent withdrawal, all subject's data collected until this time point will remain part of the study database and may not be removed.

Per protocol population

The per protocol (PP) set is defined as follows: (I) Participants that completed the study without major protocol deviations or violations (i. e. wrong product/incorrect application, missing application for more than 72 h, more than three missing study visits, inclusion/exclusion criteria not met) and (II) terminated the study regularly (study participation of at least 7 consecutive days).

For all subjects included in the full analysis set but not in the PP set, the reason for exclusion will be stated in the study report per group.

Safety analysis set

The safety population comprises all patients. Due to blinding, it doesn't matter whether they received one dose of the product or not.

Nr.	Inclusion criteria	Variable name	Comment
1	Geriatric patients or residents (≥ 65 years) staying/living in one of the participating institutions	sc_0080, sc_0091	sc_0091 for age; see sc_0020 at mnppid_visit for detailed info
2	Being incontinent of urine and stool	sc_0100	
3	Expected minimum length of stay of 14 days	sc_0110	
4	Intact skin with no clinical signs of IAD or intact skin with early clinical signs of IAD but without clinical signs of infection (GLOBIAD category 1 A)	sc_0121	Check sc_0122 for IAD category
5	Written informed consent	sc_0130	
Nr.	Exclusion criteria	Variable name	Comment/Analysis
1	Residents/patients at the end of life	sc_0140	
2	Residents/Patients with skin loss due to IAD (GLOBIAD category 2 A) and/or signs of clinical infection in the IAD area (GLOBIAD category 1 B or 2 B)	sc_0150	
3	Any other skin condition or wounds (at investigational areas of the skin) requiring additional treatment (including but not limited to pressure ulcers, intertrigo, infection)	sc_0160	
4	Known hypersensitivity or allergy to silicones and/or topical leave-on products	sc_0170	
5	Topical treatments in the IAD area.	sc_0180	

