Intervention(s)	
 • Experimental intervention I: Standardized mild skin cleansing regimen and daily topical application of a film-forming skin protectant at the exposed skin areas. • Experimental intervention II: Standardized mild skin cleansing regimen and daily topical application of a hydrophobic skin protectant at the exposed skin areas. • Control intervention: Standardized mild skin cleansing regimen without application of an additional skin protectant.
Duration of treatment	
 • Duration of intervention per patient: 14 days • Follow-up per patient: 14 days
Statistical methods	
Efficacy: The endpoints will be compared descriptively between the three groups. No confirmatory statistical tests will be conducted.
 
Description of the primary efficacy analysis and population: The intention-to-treat (ITT) principle will be applied, including all subjects that were allocated to a study group.
 
Safety: AEs, SAEs, incidents and serious incidents will be listed per patient and for the total trial.

II. TABLE OF CONTENTS

I.	Summary	2
II.	Table of contents	5
III.	Tables and Figures	8
IV.	List of Abbreviations.....	9
V.	Administrative Information	10
1.	Introduction	12
1.1	Background and rationale	12
1.2	Objectives	13
1.3	Trial design.....	13
2.	Methods: Participants, interventions, and outcomes	14
2.1	Study setting	14
2.2	Eligibility criteria	14
2.2.1	Institutional level.....	14
2.2.2	Resident/patient level	14
2.3	Interventions	15
2.3.1	Qualitative interview part	18
2.3.2	Criteria for discontinuing	18
2.4	Education	19
2.4.1	Trainings	19
2.4.2	Materials.....	19
2.5	Strategies to improve compliance and adherence to the study protocol	20
2.6	Concomitant care and interventions	20
2.7	Outcomes and variables	20
2.7.1	Initial skin assessment.....	26
2.7.2	Mexameter measurement	26
2.7.3	Resident/Patient reported outcome measures	26
2.7.4	Participants Timeline.....	28
2.8	Sample Size	30
2.8.1	Whole trial.....	30

2.8.2	Interview Part	30
2.9	Recruitment	30
2.9.1	Institutional Level	30
2.9.2	Participant Level	30
3.	Methods: Assignment of interventions	31
3.1	Sequence generation	31
3.2	Allocation concealment mechanism	31
3.3	Blinding	31
4.	Methods: Data collection, management, and analysis	32
4.1	Data collection methods	32
4.1.1	Skin assessment	33
4.1.2	Skin measurements	33
4.1.3	Other trial data	33
4.2	Data management	36

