2.3 INTERVENTIONS

Included participants of all three groups receive a standardized skin cleansing regime consisting of cleansing of the skin with water and the addition of a mild cleansing product. Cleansing is done using disposable washing mitts. To remove possible residual stool from the skin, an additional skin oil can be used. After subsequent gentle drying of the skin, elastic disposable breathable incontinence pants are put on. This is considered as 'standard incontinence care'. In order to ensure the greatest possible standardization and uniformity, the same predefined products and procedures are used for all participants. The required products for the participants will be provided by the investigators and are listed in Table 1.

After baseline visits, included residents/patients will be randomly assigned on Day 0 to one of the following three study arms:

- **Study arm 1 (Experimental intervention I):** Standard incontinence care with additional daily topical application of a film-forming leave-on skin protectant (ESENTA™ Hautschutz Spray) that builds a protective layer on the surface of the skin
- **Study arm 2 (Experimental intervention II):** Standard incontinence care with additional daily topical application of a lipophilic leave-on skin protectant (Hydrophobes Basisgel DAC) that forms a hydrophobic physical barrier on the skin
- **Study arm 3 (Control group):** Standard incontinence care alone, no additional intervention in the control group

The interventions are described in detail according to the template for intervention description and replication (TIDieR) checklist [17] in Table 1. The items 10 and 12 do not apply for study protocols and are therefore not listed in the table [17].

Table 1: Description of interventions according to the template for intervention description and replication (TIDieR) [17].

Item	Experimental intervention I	Experimental intervention II	Control group
1. Brief name	Film-forming leave-on skin protectant for IAD prevention	Hydrophobic leave-on skin protectant for IAD prevention	No skin protectant

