3.3 BLINDING

Due to the nature of the intervention, involved caregivers and participants will not be blinded. In addition, the person of the study team who reviews the diaries and verifies the correct performance of study-related procedures by nurses is also not blinded. Because the diaries provide information about assignment to the study arm, blinding of the reviewer is not possible due to the given circumstances. In order to enhance the internal validity, every visit will be performed by two members of the study team.

Member 1 of the study team performs the following tasks:

- (I) Conduct of the study visit and its related tasks as listed in Table 3 under the section "Clinical skin assessment" (including assessment of IAD-related pain, itch, patient satisfaction as well as the instrumental measurement of the erythema). Member 1 **does not conduct** any part of the assessment regarding the condition of the skin, which includes GLOBIAD IAD categorization as well as the visual inspection of erythema, erosion and maceration.
- (II) Conduct of monitoring activities as described in Table 1 under the section "11. How well".

Member 2 ("outcome assessor") of the study team is blinded and does the skin condition-related assessments only (including GLOBIAD IAD categorization as well as the visual inspection of erythema, erosion and maceration). The blinded person documents the results of the skin assessment on a separate "Skin Assessment Data Collection Form" (see **Fehler! Verweisquelle konnte nicht gefunden werden.**), independently from the main CRF (see **Fehler! Verweisquelle konnte nicht gefunden werden.**). This procedure is necessary to prevent accidental unblinding of the outcome assessor by trial group-specific information collected in the main CRF. The Skin Assessment Forms will be reintegrated into the main CRF after the respective participant has completed the study or ended its participation.

The data manager will be blinded throughout the period of data entry and verification until data base closure. The trial statistician will be blinded during statistical analysis.

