4.4 ANALYSIS POPULATION

The statistical analysis will be based on the ITT principle, this includes the whole study population and is considered as the 'full analysis set'. The IIT analysis bases on the initial treatment intent. The analysis contains all participants that met the inclusion criteria and were randomized, irrespective of possible protocol deviations, discontinuation of the study treatment or withdrawal from the study by the subject. Participants that die, discontinue participation or leave the institution during the study period will be analyzed until that time point (early termination). As only exception, the following reasons cause an exclusion of participants from the full analysis set: (I) No treatment was applied at all or (II) there are no data available after the subject's randomization. Subjects excluded from the full analysis set will be mentioned in the study report and reasons for exclusion will be documented per group. In case of consent withdrawal, all subject's data collected until this time point will remain part of the study database and may not be removed. This will be clearly stated in the ICF.

An additional per protocol (PP) analysis will be performed. The parameters for inclusion in the PP analysis set are defined as follows: **(I)** Participants that completed the study without major protocol deviations or violations (i. e. wrong product/incorrect application, missing application for more than 72 h, more than three missing study visits, inclusion/exclusion criteria not met) and **(II)** terminated the study regularly (study participation of at least 7 consecutive days). For all subjects included in the full analysis set but not in the PP set, the reason for exclusion will be stated in the

study report per group. As the ITT analysis is intended to preserve the original randomization and to avoid potential bias due to exclusion, the PP analysis aims to analyze the possible effects of the intervention administered under optimal conditions. Therefore, both analyzes are a necessary component to determine the feasibility of the applied procedures as well as possible effects of the intervention. Especially with regard to planning of a subsequent confirmatory trial.

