2.2 Application

The primary efficacy analysis will be done using the FAS including estimated values from multiple imputations for missing values (ITT framework). Participants that die, discontinue participation or leave the institution during the study period will be analyzed until that time point (early termination).

An additional analysis of the primary efficacy variable in the PP analysis set will be used as sensitivity analysis. The safety analysis includes calculation of frequencies and rates of adverse and serious adverse events in the safety analysis set.

As the ITT analysis is intended to preserve the original randomization and to avoid potential bias due to exclusion, the PP analysis aims to analyze the possible effects of the intervention administered under optimal conditions. Therefore, both analyzes are a necessary component to determine the feasibility of the applied procedures as well as possible effects of the intervention. Especially with regard to planning of a subsequent confirmatory trial

[figure not shown]
3 Trial centres

The study was conducted in geriatric hospitals/geriatric wards (acute care setting) of participating hospitals and in institutional long-term care facilities (nursing home setting) of the federal state of Berlin, Germany with a recruitment of n = 220 patients. Of these, 25 subjects were enrolled from acute care settings (14 EGZB; 11 Charité-ITS) and 195 subjects were recruited across 18 different nursing homes.

Nr	Participating ward	Number of patients (n)
Geriatric hospitals		
1	EGZB	14
2	Charité intern ITS	11
Nursing homes		
1	NH-01	11
2	NH-02	19
3	NH-03	5
4	NH-04	19
5	NH-05	17
6	NH-06	10
7	NH-07	6
8	NH-08	9
9	NH-09	7
10	NH-10	19
11	NH-11	4
12	NH-12	25
13	NH-13	8
14	NH-14	7
15	NH-15	3
16	NH-16	3
17	NH-17	13
18	NH-18	10

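### The ITT full analysis set drops randomised participants who received no treatment, against the protocol Summary and its own stated purpose, and the term 'treatment' is left undefined

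*Combined protocol and SAP*

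**What the plan says.** SAP 2.1 takes as its full analysis set the randomised participants who satisfied the inclusion criteria, grouped by intended treatment and kept whatever their protocol deviations, discontinuation or withdrawal. It then carves out two groups: "As only exception, the following reasons cause an exclusion of participants from the full analysis set: (I) No treatment was applied at all" and, second, those with no data after randomisation. Protocol 4.4 has the same two exceptions. SAP 2.2 assigns the primary efficacy analysis to this set.

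The protocol Summary describes the same analysis differently. ITT is applied "including all subjects that were allocated to a study group", with no exception named. SAP 2.2 and protocol 4.4 give the reason for having it: "the ITT analysis is intended to preserve the original randomization and to avoid potential bias due to exclusion".

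On delivery, protocol Table 1 has ward nurses carry out the care, and protocol 3.3 says that "involved caregivers and participants will not be blinded". All three arms receive the standardised cleansing regimen (protocol 2.3). The control arm is described as "Standard incontinence care alone, no additional intervention in the control group".

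Both documents already list missed application for more than 72 hours and unmet eligibility criteria as reasons for leaving the per-protocol set. SAP section 7 names per-protocol and complete-case analyses as the sensitivity analyses. FAS exclusions are to be reported with reasons per group.

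**The concern.** Whether any treatment was applied becomes known only after allocation, and it depends on people who know the arm. Removing participants on that basis is a post-randomisation exclusion, so the set is a modified ITT set rather than the one the Summary describes. If the people removed differ in risk from those kept, and the removal differs between arms, the arms are no longer comparable by design. No listed sensitivity analysis brings the removed participants back.

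The estimates from this set are meant to inform a possible confirmatory trial (SAP 1.1.1), and whether the regimen can be implemented is itself a research question (SAP 1.1.2). A participant who was allocated and never treated is information on that question.

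The eligibility restriction is a smaller inconsistency. The set is said to hold irrespective of protocol deviations, yet it requires the inclusion criteria to have been met, while unmet criteria are separately a per-protocol exclusion.

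**Working it through.** **1. What the first exception adds to the second.** Among people never treated, some have no data after randomisation and some do. Those without data already leave under the second exception. The first exception therefore adds only those who have post-randomisation data, which can include assessments by the blinded assessor. It discards observations and protects against nothing that the second exception does not already cover.

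**2. What 'treatment' can mean.** SAP 2.1 links each eligibility criterion to a database variable but links none to this exception and names nobody who decides it. SAP 4.4.3 lists a diary count of product applications, evaluated by an unblinded team member, but does not tie it to the FAS.

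| Reading | Product arms | Control arm |
|---|---|---|
| Protectant only | Removed if never sprayed or gelled | Taken literally, the whole arm goes; so in practice not applied |
| Whole assigned regimen, including cleansing | Removed only if never cleansed and never given product | Removed only if never cleansed |

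The first reading gives one-sided loss; the second is roughly symmetric. Protocol 2.3.2 confines its 72-hour missed-application rule to the intervention groups, which makes the first reading plausible but does not settle it.

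**3. Size.** There is no figure in the plan to reproduce: no formal sample size calculation, no assumed IAD risk and no readable count of exclusions. The stated totals are consistent (3 × 60 = 180; 3 × 70 = 210; 195 + 25 = 220). What follows is illustrative.

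Assume that the product has no effect and that only a product arm loses participants. Let p be the true 14-day risk in every arm, f the share of the product arm removed, and r the risk of those removed relative to the whole arm. All three are assumptions. Then

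retained risk = (p − f·r·p) / (1 − f), and bias = retained risk − p.

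| p | f | r | Retained risk | Bias (points) |
|---|---|---|---|---|
| 20% | 2% | 2 | 0.192/0.98 = 19.6% | −0.4 |
| 20% | 5% | 2 | 0.180/0.95 = 18.9% | −1.1 |
| 20% | 10% | 2 | 0.160/0.90 = 17.8% | −2.2 |
| 20% | 5% | 0.5 | 0.195/0.95 = 20.5% | +0.5 |
| 20% | 10% | 0.5 | 0.190/0.90 = 21.1% | +1.1 |
| 35% | 10% | 2 | 0.280/0.90 = 31.1% | −3.9 |
| 35% | 10% | 0.5 | 0.3325/0.90 = 36.9% | +1.9 |

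With r = 1 the bias is zero. If the control arm loses the same share with the same r, the two shifts cancel under the null. Over p = 10% to 35%, f = 2% to 10% and r = 0.5 to 2, the range is −3.9 to +1.9 points. If all 220 recruits were randomised 1:1:1, each arm has about 220/3 = 73, and f = 5% is about 3.7 people.

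For scale, the 95% half-width for a risk difference at 70 per arm is 1.96·√(2p(1 − p)/70): 9.9 points at p = 10%, 13.3 at 20% and 15.8 at 35%.

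**4. How much a change would recover.** The table credits the removed people with their full 14-day risk. Under protocol 2.3.2 a product-arm participant without application for more than 72 hours meets a discontinuation criterion, and SAP 2.2 analyses discontinued participants up to that time. Such a person would usually contribute only one or two follow-up visits. The table therefore tends to overstate what restoring these people would change.

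**The case against.** A reader might infer that only the two product arms can lose participants, and that product effects are therefore overstated. The documents do not support either step. The inference counts cleansing as treatment for controls but only the product as treatment for the other arms. Cleansing is part of every arm's regimen and is the whole control therapy. On a single consistent reading, either the rule is roughly symmetric or it cannot sensibly be applied to controls. Direction is also open: the bias reverses if never-treated people are at lower risk. Nor is caregiver conduct the only route, since death, transfer or withdrawal before first care could occur in any arm.

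Other points in the plan's favour stand. The trial is exploratory, with no confirmatory tests. Participants are grouped as allocated, and one application is enough to stay in. Exclusions are reported by group, and study staff review the diaries at least every second day (protocol 2.5). Eligibility is settled before randomisation, so that restriction need not depend on arm. The count may appear in the flow chart mentioned in the SAP file history, which is not readable here, and it could be zero.

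These points limit the size. They do not remove the contradiction with the Summary, and reporting exclusions by arm discloses them without restoring the outcomes. Nor do wide intervals correct a bias.

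**Conclusion.** The contradiction is established from the text: the definition in SAP 2.1 and protocol 4.4 does not match the Summary or the purpose both documents give for ITT. It is also established that the first exception discards only participants with post-randomisation data, that delivery is unblinded, and that no planned sensitivity analysis covers them.

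One-sided loss is possible but not established, because it turns on an undefined term. Any bias is of unknown direction and probably small: a few percentage points at most under the assumed p, f and r, and less than the half-width of the intervals. It is zero if nobody meets the exception. The point deserves a change because the remedy is nearly free, not because a large distortion has been shown.

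**What to change.** In SAP 2.1 and protocol 4.4:

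- Delete the no-treatment exception and the restriction to participants who met the inclusion criteria. The primary full analysis set is then all randomised participants with any post-randomisation data, analysed as allocated.
- List randomised participants without post-randomisation data by arm.
- Keep non-application and ineligibility as per-protocol exclusions only.
- Report the number never treated in each arm, stating whether this means the protectant or the whole regimen.
- Optionally, keep the present set as a sensitivity analysis, with 'treatment' defined.
- Reconcile the Summary with both sections, including the remaining no-data exception.

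The cost is a dated wording change, best made before the arm labels are opened, and at most a few participants returning to the data set. The downside is that estimated product effects may be slightly diluted by people who received no product.
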